9.8. Left Ventricular Ejection Fraction (LVEF)

The LVEF data will be listed.

9.9. ECOG Performance Status (PS)

The ECOG PS will be summarized by treatment arms and visits, and by shift tables from baseline to worst values across all visits by treatment arms.

A by-subject listing will be provided.

9.10. Interim Analysis

There will be no formal interim analyses of the data. Interim safety reviews will be conducted by an IDMC on a regular basis. Details are specified in the protocol and IDMC charter.

10. GENERAL METHODS

Summary statistics will be presented by treatment and scheduled visit, unless stated otherwise.

Unless otherwise specified, descriptive statistics for continuous data will include the number of subjects with data to be summarized (n), mean, standard deviation, median, minimum, and maximum.

Descriptive statistics for categorical/qualitative data will include frequency counts and percentages. The total number of subjects in the treatment arm will be used as the denominator for percent calculations, unless stated otherwise.

Descriptive statistics associated with time-to-event analyses will include the number of events, the number of subjects censored, 25% quartile, median, 75% quartile, and 95% CI for median. These statistics will be presented for all time-to-event analyses, unless stated otherwise.

Listings will be provided for selected endpoints. Listings will be sorted by site, treatment, and subject IDs.

10.1. General Rules

All data listings that contain an evaluation date will contain a relative study day (Rel Day).

Study days are numbered relative to the day of the first dose of study medication (designated as Day 1) for safety related outputs, and relative to the randomization date for the efficacy related outputs. The preceding day is Day -1, the day before that is Day -2, etc.

Other conventions include the following:

- Data from all study centers will be combined in the analysis, unless specified otherwise.
- Confidence intervals, if presented, will be 2-sided 95% CIs unless otherwise specified.
- All analyses and summary tables will have the analysis population sample size for each treatment group (treatment arm, overall, etc.) in the column heading (ie, number of subjects).

10.2. Unscheduled Visits and Visit Windows

Unscheduled visits will not be mapped and will not be included in the summary statistics per visit tables. However, they will be included in the data listing as well as the shift tables.

10.3. Baseline Values

Unless otherwise specified, the baseline value is defined as the value collected at the time closest to, and prior to, the start of study drug administration. In case subjects are not dosed, the latest assessment will be considered as baseline. Values collected at unscheduled visits prior to the start of the study drug administration will be included in the calculation of baseline values. In majority of cases, C1D1 assessment should be treated as the baseline as the study protocol requires assessment to be done pre-dose at C1D1. For visits after crossover, the closest

assessment prior to the start of AG-120 will be considered as the baseline for crossover data analysis.

10.4. Computing and Coding Standards

Activities will be performed using the following tools:

Table, listing, and figure production	SAS Version 9.2 or higher
Coding	
Adverse Events	MedDRA Version 21.1 or higher
Medical Histories	MedDRA Version 21.1 or higher
Prior and Concomitant Medications	WHODrug Version 2018 Q1 or higher
Grading	
AEs	CTCAE Version 4.03
Labs	CTCAE Version 4.03

10.5. Missing/Partial Dates in Adverse Events and Concomitant Medications/Therapies

Missing/Partial Start Dates:

If the stop date is non-missing and the imputed start date is greater than the stop date, the stop date will be used as the start date.

1) Missing day only

- If the month and year are the same as the month and year of the first dose date, the first dose date will be used
- If the month and year are before the month and year of the first dose date, the last day of the month will be assigned to the missing day
- If the month and year are after the month and year of the first dose date, the first day of the month will be assigned to the missing day

2) Missing day and month

- If the year is the same as the year of the first dose date, the first dose date will be used
- If the year is prior to the year of the first dose date, December 31 will be assigned to the missing fields
- If the year is after the year of the first dose date, January 1st will be assigned to the missing fields

3) Missing day, month, and year

- The first dose date will be used

If the first dose date is missing, no imputation will be performed.

Missing/Partial Stop Dates:

1) Missing day only

- The last day of the month will be assigned as the missing day

2) Missing day and month

- December 31 will be assigned to the missing fields

3) Missing day, month, and year

- The event will be regarded as ongoing

All the imputed dates will be compared against the End of Study date, death date, and data cutoff date. The earliest date will be chosen.

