7. STATISTICAL ANALYSES

Unless specified otherwise, longitudinal data will be presented by “before crossover” and “after crossover” periods, defined as:

- **“After crossover”** contain data collected after placebo subjects crossed over to AG-120. COS will be the analysis set.
- **“Before crossover”** contain AG120 arm data and the Placebo arm data up till crossover.

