9. SAFETY ANALYSIS

Unless specified otherwise, the safety data will be summarized by treatment based on SAS. Specifically, it will include placebo before crossover, AG-120 as dosed, AG-120 after crossover, and total AG-120. The total AG-120 includes all the subjects who have ever been dosed with AG-120 (that is, the sum of AG-120 as dosed and AG-120 after crossover). If a subject receives at least one dose of AG-120, the actual arm will be AG-120 as dosed. The same rule applies to the after crossover.

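### SAP 10.5 has no crossover anchor, so some adverse events that begin on AG-120 after crossover are dated back into the placebo period

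*SAP*

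**What the plan says.** Protocol 12.13 has partial adverse event dates imputed and leaves the rules to the SAP. SAP 10.5 supplies them, for adverse events and concomitant medications together. For start dates that are not before the first dose:

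- Day missing, same month as first dose: the first dose date. Day missing, later month: "the first day of the month will be assigned to the missing day".
- Day and month missing: "If the year is the same as the year of the first dose date, the first dose date will be used". In a later year, "January 1st will be assigned to the missing fields".
- Fully missing: "the first dose date will be used".

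A known stop date caps the imputed start. Beyond that, "All the imputed dates will be compared against the End of Study date, death date, and data cutoff date", and the earliest is kept. The date of first AG-120 dose after crossover does not appear.

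The outputs nevertheless depend on that date. SAP 9 says of the safety summaries that "it will include placebo before crossover, AG-120 as dosed, AG-120 after crossover, and total AG-120". SAP 7 defines the before-crossover period to "contain AG120 arm data and the Placebo arm data up till crossover". SAP 7.5 places concomitant medications and procedures in the after-crossover table when they start on or after the AG-120 crossover start. SAP 10.3 and 9.4 re-set baseline at the same point.

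**The concern.** At the first dose, the rule protects the treatment period: an event that could have started in the month or year of first dose is placed on treatment. At crossover, the second time treatment begins, there is no such protection. An event that began on AG-120 may then be counted against placebo. At stake are three safety columns: placebo before crossover (too high), AG-120 after crossover (too low) and total AG-120 (too low). All three shifts flatter the drug. Because SAP 7.5, 9.4 and 10.3 use the crossover start where it is needed, its absence from 10.5 looks like an omission rather than a choice.

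**Working it through.** The documents give no figure for this point, so there is none to reproduce. The check applies the 10.5 rule as written.

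**Step 1: direction.** Take any event that starts on or after the first dose. Each branch returns the first dose date, the 1st of the event's month or 1 January of its year, and none of these is later than the true onset. The stop-date, end-of-study, death and cutoff limits can only move the date earlier. So an event with true onset on placebo cannot be pushed past crossover, while one with true onset on AG-120 can be pulled back before it.

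**Step 2: which events move.** Illustrative dates:

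| First dose | Crossover | True onset | Known part | Imputed | Period |
|---|---|---|---|---|---|
| 10 Jan 2018 | 18 Apr 2018 | 25 Apr 2018 | month, year | 1 Apr 2018 | placebo (wrong) |
| 10 Jan 2018 | 18 Apr 2018 | 6 May 2018 | month, year | 1 May 2018 | AG-120 (right) |
| 10 Jan 2018 | 18 Apr 2018 | 6 May 2018 | year | 10 Jan 2018 | placebo (wrong) |
| 10 Nov 2017 | 14 Feb 2018 | 6 Mar 2018 | year | 1 Jan 2018 | placebo (wrong) |
| 10 Aug 2017 | 14 Nov 2017 | 20 Feb 2018 | year | 1 Jan 2018 | AG-120 (right) |
| 10 Aug 2017 | 14 Nov 2017 | 20 Feb 2018 | none | 10 Aug 2017 | placebo (wrong) |

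**Step 3: share of AG-120-onset events moved, given the missing pattern.** Assumptions not in the documents: first doses spread evenly over 365 days; crossover 42, 91 or 182 days later; onset uniform over the first D days on AG-120; no stop date that changes the result; events split by imputed start date.

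- Day missing: only the rest of the crossover month is affected, and nothing if crossover is on the 1st. For a month of L days the affected days sum to L(L − 1)/2. Over a year that is 7 × 465 + 4 × 435 + 378 = 5,373, and 5,373/365 = 14.72 days on average. The share is 14.72/D.
- Year only: the share is 1 − (D + 1)/730, because events in a calendar year after crossover are placed correctly.
- Fully missing: all.

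| D (days on AG-120) | Day missing | Year only | Fully missing |
|---|---|---|---|
| 30 | 49% | 96% | 100% |
| 91 | 16% | 87% | 100% |
| 182 | 8% | 75% | 100% |

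Full enumeration over the 365 first-dose dates gives the same values for all three crossover timings.

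**Step 4: effect on a table.** Protocol 8.1 plans 62 placebo subjects. One subject wrongly counted for a preferred term adds 1/62 = 1.6 points to placebo. SAP 9.1 lists common events at 5% in any group. Since 3/62 = 4.8% and 4/62 = 6.5%, one subject can carry a term over that line.

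**Step 5: what a blanket AG-120 anchor would do.** If every date compatible with crossover were set to the first AG-120 dose, none of the AG-120-onset events would be misplaced. But of the events with true onset on placebo, 8% to 35% with day missing, 75% to 94% with year only and 100% with no date would move to AG-120 (crossover at day 182 to day 42).

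**The case against.** The SAP does not say by which date an adverse event is placed before or after crossover. SAP 7 speaks of data collected after crossover. Events are recorded at every visit and crossover subjects restart the visit schedule, so the recording period could decide. It might also be said that the first dose date in 10.5 should be re-read as the first AG-120 dose for after-crossover outputs, as is done for baseline, and that SAP 9 ends by carrying a rule over to the after-crossover period.

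Neither reading closes the gap. The SAP 9 sentence concerns which arm a subject is analysed in, not dates. Re-reading the anchor is circular, because the period must be known before the anchor can be chosen. SAP 9.1 defines treatment-emergent events by when they begin or worsen, which makes start date the natural criterion, and SAP 7.5 makes it explicit for concomitant medications. What stands is that, for adverse events, the consequence rests on an unstated but natural reading.

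Three limits also stand. A reader might infer that every undated event starting on AG-120 goes to placebo. The documents do not support that: a day-missing event in a month after the crossover month, or a year-only event in a year after crossover, is placed correctly. A reader might infer that each record shifts placebo incidence by 1.6 points. SAP 9.1 counts a subject once per preferred term, so a subject who already had that term on placebo adds nothing, and 1.6 points is a ceiling. Finally, Protocol 11.2 requires an onset date for every event and Protocol 13.6 has discrepancies queried, so such records should be few.

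**Conclusion.** The point holds in limited form. Followed literally, SAP 10.5 dates AG-120-onset events into the placebo period in cases (a) day missing in the crossover month, unless crossover was on the 1st; (b) year only, in the first-dose or crossover year; and (c) fully missing. It never does the reverse.

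This assumes that the first dose date means the first dose of study drug and that events are split by imputed start date. The ceiling is 1.6 points of placebo incidence per affected subject per preferred term, taking the planned 62 as the number dosed. The after-crossover and total AG-120 columns lose that subject only if no other event of the same term is dated to AG-120. The documents give no rate of missing dates, so the total effect cannot be computed; it is likely small. The randomised AG-120 column, PFS, OS and ORR are unaffected. This is a minor correction, worth making because the error is one-directional and favours the drug.

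**What to change.** Add to SAP 10.5 that, for subjects who cross over, the first AG-120 dose date is a second anchor, applied in stages:

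1. Day missing, with month and year equal to those of the first AG-120 dose: impute that dose date, unless the stop date or the visit or eCRF period of recording shows onset before crossover.
2. Adverse events with year only or no date: assign the period from the stop date and the recording visit or eCRF period. Use the first AG-120 dose date only as a fallback when these do not settle it. Add a sensitivity table under the current 10.5 rule.
3. Concomitant medications with year only or no date: assign the period from the recording visit or eCRF period and the stop date, with no fallback to AG-120. Moving an undated medication to the AG-120 period is not conservative in any useful sense.

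State in SAP 9.1 that adverse events are placed before or after crossover by start date, imputed where necessary.

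The cost is a short programming rule and one extra table, before database lock. The downside is that a few true placebo-period events whose dates cannot be resolved would be counted under AG-120. The staging is there to keep that number small, since a blanket anchor would move most year-only placebo events and all fully undated ones.

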10.6. Missing/Partial Dates in On-study Anticancer Therapies

On-study anticancer therapy with start dates that are completely or partially missing will be imputed as follows:

1. If the start date has month and year but day is missing, the 15 of the month will be imputed.
2. If the start date has year, but day and month are missing, July 1 will be imputed.

On-study anticancer therapy with stop dates that are completely or partially missing will be imputed as follows:

1. If the stop date has month and year but day is missing, the last day of the month will be assigned.
2. If the stop date has year, but day and month are missing, December 31 will be assigned.
3. If the stop date misses day, month and year, the event will be considered as ongoing.

If the imputed date is before the last dosing date, the last dosing date will be used as the on-study anticancer therapy start date. If the imputed date is after the death date then the death date will be used. If the imputed stop date is before start date, the stop date will be used as the start date.

This imputation rule will only be used in efficacy endpoints derivation (such as PFS, OS). The listing of post-study anticancer therapy will not apply imputation rules.

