5. SAMPLE SIZE ESTIMATION

A total of approximately 186 subjects will be needed for the study.

The primary objective of the study is to demonstrate the improvement in PFS by IRC assessment for subjects receiving treatment with AG-120 as compared to subjects receiving placebo.

Assuming a hazard ratio (HR) of 0.5 for PFS (equivalent to a median PFS of 3 months in the placebo arm vs. 6 months in the AG-120 arm, assuming an exponential distribution), a total of 131 PFS events are required to provide 96% power at a 1-sided alpha of 0.025 level of significance to reject the null hypothesis using a stratified log-rank test. Based on this, a total of approximately 186 subjects will need to be randomized in a 2:1 ratio to the AG-120 and placebo arms, respectively, assuming approximately a 22% dropout rate, an approximate 26-month randomization period, and an additional 6-month follow-up for PFS after the last subject is randomized. Therefore, the primary analysis of PFS will occur at approximately 6 months after the last subject is randomized.

Overall survival will be analyzed twice, once at the time of the final analysis for PFS and once at the occurrence of 150 OS events (final analysis for OS, which will occur at approximately 24 months after the last subject is randomized). Assuming an HR of 0.67 for OS (median OS of 8 months in the placebo arm vs. 12 months in the AG-120 arm, assuming an exponential distribution), a total of 150 OS events will provide 64% power at a 1-sided alpha of 0.025.

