8.1.2. Additional Analyses of PFS

The following analyses of PFS will be performed by treatment arms:

For IRC assessments:

- Stratified log-rank test and Cox regression based on all scans read by IRC prior to crossover, including the scans after local PD from subjects who were originally assigned to AG-120 and continued to stay after unblinding.
- Stratified log-rank test and Cox regression based on PPS set.
- Unstratified log-rank test (one-sided) to compare the two treatment arms. An unstratified Cox regression will be used to estimate the HR (AG-120/placebo) with its 95% CI.
- Subgroup analysis with unstratified log-rank test and unstratified Cox regression model. The HR (AG-120/placebo) with its 95% CI will be displayed for all subgroups graphically in a forest plot. The subgroups will include:
 - The actual number of prior line of therapies in advanced setting (1 vs. ≥ 2)
 - Gender (female vs. male)
 - Extent of disease at screening (locally advanced vs. metastatic)
 - If subject had both local and metastatic, it would be considered as metastatic
 - Intrahepatic vs. extrahepatic
 - Perihilar will be included in extrahepatic category
 - ECOG at baseline (0 vs. ≥ 1)
 - Regions (North America vs. Europe vs. Asia)

In addition, the following exploratory analyses may be performed:

- PFS analysis by excluding subjects who progressed early (≤ 47 days within randomization date, i.e., 6 weeks + 5 days of scan visit window).
- The Cox regression model by including treatment, sum of target lesions at baseline, and other possibly related parameters in covariates.

For Investigator assessments:

- Stratified log-rank test (one-sided) will be utilized to compare the two treatment arms. A stratified Cox regression model will be used to estimate the HR (AG-120/placebo)

with its 95% CI. The same censoring rule as described for the primary PFS based on IRC assessment will be used.

In addition, the concordance of PFS between investigator and IRC assessment will also be summarized by treatment arms and overall.

Table 1: Handling of Missing Response Assessment and Censoring for the Primary Analysis of PFS

Situation	Date of Censoring
No baseline assessment and no death.	Date of the randomization
Alternate anticancer systemic treatment started before documented progression (PD) or death.	Date of last adequate assessment prior to the start of anticancer treatment ¹
No adequate post-baseline assessment and no death.	Date of the randomization

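### SAP 10.6 imputes a partial new-therapy start date without looking at documented progression, so a subject whose last dose preceded the PD scan can lose a real PFS event

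*SAP*

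**What the plan says.** SAP 10.6 covers partial start dates of on-study anticancer therapy. For a missing day: "If the start date has month and year but day is missing, the 15 of the month will be imputed". With only the year known, July 1 is used. Two bounds follow. The lower one reads "If the imputed date is before the last dosing date, the last dosing date will be used as the on-study anticancer therapy start date"; the upper one replaces any imputed date after death with the death date. Neither involves PD. The section limits the rule to deriving efficacy endpoints and names PFS among them.

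The date feeds SAP Table 1, in 8.1.2. One censoring situation there is "Alternate anticancer systemic treatment started before documented progression (PD) or death", and such a subject is censored at the last adequate assessment before the therapy start. The introduction to SAP section 8 also drops tumor assessments made after new therapy began from the response-related summaries. Investigator PFS (8.1.2) and duration of response (8.6) use the same censoring.

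The protocol makes PD followed by new therapy the usual order. Section 9.13.3 requires study treatment to stop if other anticancer therapy is needed. Under section 7.1, scanning in PFS follow-up continues until progression or the start of new therapy.

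**The concern.** A rule meant to fill in a missing day or month can decide whether a documented progression counts. If the imputed start lands before the PD scan, the event is deleted and the subject is censored at a scan taken shortly before a known progression. Such censoring is informative. It affects the primary endpoint, and an incomplete form entry triggers it.

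The last-dose floor protects a subject only if the last dose was on or after the PD scan date. The plan foresees subjects for whom it was not: those who stop for another reason and progress in PFS follow-up (protocol 7.1 and 8.5.1), and those whose dose was held and never resumed (9.8.1.1 and 9.10.1). Subjects randomized but never dosed, whom SAP 7.1 counts, have no floor at all.

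**Working it through.** **1. The plan's own figure.** SAP section 5 assumes HR 0.5 and 2:1 allocation and states "a total of 131 PFS events are required to provide 96% power at a 1-sided alpha of 0.025 level of significance". Schoenfeld's formula gives power = Φ(√(d·p·(1−p))·|ln HR| − 1.96) with p = 2/3. For d = 131: √(131 × 2/9) × 0.693 = 3.740; 3.740 − 1.960 = 1.780; Φ = 96.2%. The stated figure is reproduced.

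**2. The rule on worked dates.** In every row the true order is PD, then therapy.

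| PD scan | Last dose | True start | Known | Imputed start | Result |
|---|---|---|---|---|---|
| 20 Jun | 13 Jun | 28 Jun | month, year | 15 Jun | event lost |
| 20 Jun | 18 Jun | 28 Jun | month, year | 18 Jun (floor) | event lost |
| 20 Jun | 20 Jun | 28 Jun | month, year | 20 Jun (floor) | event kept |
| 20 Jun | 25 Jun | 28 Jun | month, year | 25 Jun (floor) | event kept |
| 20 Sep | 10 May | 5 Oct | year | 1 Jul | event lost |
| 20 Sep | 22 Sep | 5 Oct | year | 22 Sep (floor) | event kept |

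In the fifth row the imputed start is 81 days before PD, so any progression-free scans in between are ignored as well.

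**3. Who is exposed.** If the last dose is on or after the PD scan, the floor puts the imputed start on or after PD and the loss is 0% under either rule. SAP section 8 excludes IRC reads after local PD from the primary analysis, so a counted IRC PD is never later than local PD. Dosing up to the local PD scan is therefore enough.

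**4. Share reversed among exposed subjects.** Assumptions, none of them in the documents: a partial date; PD uniform over the year; last dose uniform over 0-14 days before PD; therapy starting g days after PD.

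- *Day missing.* Reversal needs PD and start in the same month, with PD after the 15th, so g cannot exceed 15 days. For a given g up to 14 the share is about (15.44 − g)/30.44, using a mean month of 30.44 days. With g averaging 7.5 (1-14 days): 7.94/30.44 = 26%.
- *Only year known.* PD must fall after July 1 and the start in the same year: (183 − g)/365. With g averaging 7.5: 175.5/365 = 48%.
- One of the 15 last-dose values (0 days before PD) is protected, so multiply by 14/15.

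| Therapy start after PD | Day missing | Only year known |
|---|---|---|
| 1-14 days | 24% | 45% |
| 1-28 days | 12% | 43% |
| 7-42 days | 3% | 41% |
| 14-56 days | 0.1% | 38% |

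Counting every date in a year gives the same figures.

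**5. Effect on power.** Five events lost (126): √(126 × 2/9) × 0.693 = 3.668, power 95.6%. Ten lost (121): 3.594, power 94.9%. At the highest shares, losing ten events would take about 10/0.243 = 41 exposed subjects with a missing day, or 10/0.449 = 22 with only the year known.

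**The case against.** The strongest reply is that the plan already has a safeguard and few subjects fall outside it. A reader might take the last-dose sentence as pulling start dates back and so causing the loss. It does not: it applies only when the imputed date is earlier than the last dose, so it moves dates later and limits the error. Treatment ordinarily runs until progression and scans follow a fixed calendar (protocol 7.1), so most subjects should still be dosed at the PD scan. That includes those who then stop because of progression. Stopping for another reason also calls for a scan at the end-of-treatment visit, which protocol 10.1 puts within 5 days of the last dose when dosing was not delayed. A PD found there may escape the reversal, and a clean scan there can shorten the distance to the censoring date. Incomplete entries are queried (protocol 13.6), so year-only dates should be uncommon. All of this stands, and it limits the number affected. It does not help the subjects who remain exposed, because nothing else in either document checks the imputed date against PD.

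A second reply is that the rule errs both ways: it can place a true earlier switch after PD and count an event that should be censored. A floor at PD also makes a therapy date depend on the outcome, and may give one subject different start dates in the IRC and Investigator analyses. This is a fair cost. It is small because scanning for PFS stops at new therapy, so a counted PD normally came before the switch.

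**Conclusion.** The rule is wrong as written for a narrow group: subjects with a partial therapy start date whose last dose came before the PD scan. Followed exactly, it can turn a documented primary event into earlier, informative censoring. The number affected cannot be derived from the documents. Few lost events and little loss of power are to be expected, so the case for change rests on the integrity of the endpoint derivation.

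Two stronger readings are not supported. First, a reader might infer a bias between arms, because AG-120 subjects may be treated beyond progression while placebo subjects are dosed later only if they cross over. But a placebo subject dosed through the PD scan who never crosses over is equally protected, and nothing in the documents shows that a last dose before PD is more common in one arm. Second, the 24% and 38-45% figures might be read as shares of all subjects who progressed and then changed therapy. They apply only to exposed subjects under the assumed timings, and the missing-day figure is close to zero once therapy starts more than two weeks after PD.

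One point stays open. SAP 10.6 does not say whether the last dosing date of a crossover subject includes AG-120 after crossover; their protection depends on it if their last placebo dose preceded the PD scan.

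**What to change.** Add to SAP 10.6: where the known parts of the start date are compatible with a start on or after the first documented PD used in that analysis (IRC PD for the IRC analysis, Investigator PD for the Investigator analysis), the imputed start may not be earlier than that PD date; otherwise the present rule applies. State whether the last dosing date includes AG-120 after crossover. The section also announces imputation for completely missing start dates but gives no rule for them; supply one in the same edit.

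The cost is a few lines of SAP text and a small change to the derivation program, with no new data. SAP section 1 has the plan finalized before database lock, so this can be settled without knowledge of results. The downside is that a subject who truly switched shortly before PD, within the same known month or year, would be counted as an event. Report by arm how many subjects' event or censoring status depends on the imputation, so that readers can judge its weight.
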